ULN	Upper Limit of Normal
VEGF	Vascular Endothelial Growth Factor

List of Key Terms

Terms	Definition of terms
Baseline	Observed values/findings which are regarded observed starting point for comparison.
Intervention	The drug, therapy or process under investigation in a clinical study that is believed to have an effect on outcomes of interest in a study. (e.g., health-related quality of life, efficacy, safety, pharmacoeconomics).
Screening period	Period of time before entering the investigational period, usually from the time of starting a subject signing consent until just before the test drug or comparative drug (sometimes without randomization) is given to a subject.
Randomization	The process of assigning trial subjects to treatment or control groups using an element of chance to determine assignments in order to reduce bias.
Screening	A process of active consideration of potential subjects for enrollment in a trial.
Screen failure	Potential subject who did not meet one or more criteria required for participation in a trial.
Study period	Period of time from the first site initiation date to the last site completing the study.
Variable	Any quantity that varies; any attribute, phenomenon or event that can have different qualitative or quantitative values.

1 INTRODUCTION

This Statistical Analysis Plan (SAP) contains a more technical and detailed elaboration of the principal features of the analysis described in the protocol, and includes detailed procedures for executing the statistical analysis of the primary and secondary endpoints and other data.

The SAP will be drafted before first subject enrolled and finalized before the database soft lock. If needed, revisions to the approved SAP may be made prior to database hard lock. Revisions will be version controlled.

This statistical analysis plan is coordinated by the responsible biostatistician of APGD-US. Any changes from the analyses planned in the SAP will be justified in the Clinical Study Report (CSR).

Prior to database hard lock, a final review of data and Table, Listings, and Figures (TLFs) meeting will be held to allow a review of the clinical trial data and to verify the data that will be used for analysis set classification. If required, consequences for the statistical analysis will be discussed and documented. A meeting to determine analysis set classifications may also be held prior to database hard lock.

2 FLOW CHART AND VISIT SCHEDULE

Informed Consent	→	Screening Period (Days -21 to -1)	→	Day 1 Pre-dose Confirmation of eligibility criteria and enrollment	Treatment Period (Day 1 - until a discontinuation criterion is met) Visits at Weeks 3, 5, then every 4 weeks Tumor Assessment will be done every 8 weeks (+/- 7 days) and measurement of HBV viral levels (for subjects with HBV) to be done per Institution SOC	End of Treatment Visit (within 7 days after last dose)	Follow-up Period (Approx.30-days after last dose of study drug, then q30 days to collect information on survival and subsequent therapies)
------------------	---	--------------------------------------	---	---	--	--	--

Abbreviations: HBV= hepatitis B virus, q = every, SOC = standard of care

Assessments	Screen	Treatment Period						Unscheduled Visit	Follow-up Period		
		1	3	5	9	13	17 + Q4 Weeks		EOT	30D FU¹	Long Term FU¹
Study Week/Visit	-3 to -1										
Study Day	-21 to -1	1	15	29	57	85	113+	N/A	≤ 7D after last dose	30D after last dose	Q30 days
Window (days)	N/A	0	+/-3	+/-3	+/-3	+/-3	+/-3	N/A	N/A	+10	+10
Informed Consent	X										
Inclusion/Exclusion Criteria	X	X									
Return and/or Dispense of study drug		X	X	X	X	X	X	X [OPT]	X		
Concomitant Medications ²	X	X	X	X	X	X	X	X	X	X	
Demographics, Medical and Disease History	X										
BCLC Staging	X										
Child-Pugh Classification	X										
HBV/HCV Status ³	X										
Tumor Assessment ⁴	X	To be performed Q8Weeks (+/- 7 D) From Day 1						X [OPT]			
Height	X										
Weight	X	X		X	X	X	X	X [OPT]	X		
Vital Signs	X	X	X	X	X	X	X	X [OPT]	X		
Adverse Events ⁵	X	X	X	X	X	X	X	X	X	X	
Clinical Laboratory Tests ⁶	X ⁶	X ⁷	X	X	X	X	X	X [OPT]	X		
Urine Pregnancy Test ⁹	X	X		X	X	X	X	X [OPT]	X		
Physical Examination	X	X	X	X	X	X	X	X [OPT]	X		
12-Lead ECG	X				X			X [OPT]	X		
ECOG PS	X	X	X	X	X	X	X	X [OPT]	X		
Alpha-fetoprotein	X	X ⁶	X	X	X	X	X	X [OPT]	X		
HBV Viral Levels (if applicable)	X	To be done per SOC or as clinically indicated									
Pharmacokinetic Sample ¹⁰			X	X	X			X [OPT]			
		X				X					
Tumor Tissue Collection ¹²	X										
Blood Samples for PGx Biobanking (optional)		X									
Survival and Subsequent Treatment			X	X	X	X	X		X	X	
		X		X	X	X	X				

Footnotes appear on next page

Abbreviations: BCLC = Barcelona Clinic Liver Cancer, D = day(s), ECG = electrocardiogram, ECOG PS = Eastern Cooperative Oncology Group Performance

Status, EOT = end of treatment, FSH = follicle-stimulating hormone, FU = follow-up, HBV = hepatitis B virus, HCV = hepatitis C virus, N/A = not applicable, OPT = optional, PGx = pharmacogenomics, Q = every, SOC = standard of care

1. Phone call may be conducted if subject is unable to travel. Long-term follow-up will occur for up to 2 years, until death or subject withdraws consent or final analysis.
2. Medications taken within 14 days before the Screening visit and up to the 30-day Follow-up Visit will be collected.
3. HBV/HCV status will be assessed at Screening. HBV should be assessed using an assay for hepatitis B surface antigen. HCV testing should be performed using an antiHCV antibody assay (enzyme immunoassay [EIA] or enhanced chemiluminescence immunoassay [CIA]).
4. Computed tomography (CT)/magnetic resonance imaging (MRI) of the chest/abdomen/pelvis as well as any other anatomical region appropriate for the subject's disease must be performed within 28 days prior to day 1. Results from CT/MRI assessments performed prior to consent and within 28 days of day 1 may be used for Screening if available. Subsequent scans will be done every 8 weeks (+/- 7days) from Day 1 until treatment discontinuation criterion is met. To ensure comparability, the Screening and subsequent assessment should be performed using identical techniques.
5. Adverse events will be collected from the time of informed consent through the 30-day Follow-up Visit or through the day prior to the initiation of new antineoplastic treatment or investigational agent, or whichever comes first.
6. Clinical laboratory assessments include hematology, chemistry, coagulation, viral load (if applicable), pregnancy and urinalysis (urine dipstick). Lab parameters to be analyzed are listed under Appendix 12.8 Laboratory Assessments.
7. FSH testing is also required for postmenopausal women who are < 55 years of age at Screening.
8. Day 1 clinical laboratory tests do not need to be repeated if Screening labs were performed within 7 days prior to Day 1.
9. Urine pregnancy test will be performed in women of childbearing potential. Testing at treatment visits must occur prior to study drug administration.
10. Pharmacokinetic samples will be collected prior to dosing. Subjects will be instructed to record on a diary the date and time that study drug was taken on the 2 days before the visit and not to take study drug until after the pharmacokinetic sample is collected. The date and time that the subject took the previous 2 doses of study drug should be recorded, even if the most recent dose was inadvertently taken earlier the same day.
11. [REDACTED]
12. Subject has available formalin-fixed, paraffin-embedded tumor specimen with adequate viable tumor cells in a tissue block or unstained serial slides accompanied by an associated pathology report prior to enrollment. Archival or fresh biopsy tissue is required. Ensure that subject meets all other study entry criteria prior to performing a biopsy (as applicable).
13. [REDACTED]

3 STUDY OBJECTIVE(S) AND DESIGN

3.1 Study Objective(s)

3.1.1 Primary Objective

To evaluate the efficacy of enzalutamide as compared to placebo in subjects with advanced hepatocellular carcinoma (HCC), as measured by overall survival (OS).

3.1.2 Secondary Objectives

- To evaluate Progression Free Survival (PFS) of enzalutamide as compared to placebo in subjects with advanced HCC.
- To evaluate the safety of enzalutamide in subjects with advanced HCC.
- To evaluate the pharmacokinetics (PK) of enzalutamide and the active metabolite N-desmethyl enzalutamide in subjects with advanced HCC.

3.1.3 Exploratory Objectives

- [REDACTED]
- [REDACTED]
- [REDACTED]
- [REDACTED]

3.2 Study Design

This is a multicenter, randomized, double-blind, placebo-controlled phase 2 study evaluating the efficacy, safety, and tolerability of enzalutamide monotherapy in approximately 144 subjects in Europe, Asia and North America with HCC of any etiology who have progressed on or were intolerant to sorafenib or other anti-VEGF therapy in the advanced setting. Each region will have no more than 70% of overall subjects enrolled. Enrollment may be limited by the sponsor in any region or country in order to have representation of the patient populations from all 3 regions as there may be a difference in responses to treatment or tolerability.

The study will consist of a Screening Period, Treatment Period and a Follow-up Period. Eligible subjects will be stratified by geographic region (Asia versus other) and Eastern Cooperative Oncology Group (ECOG) performance status (0 versus 1) and randomized in a 2:1 ratio to receive enzalutamide 160 mg/day or placebo until disease progression, unacceptable toxicity, or any other discontinuation criterion is met. Study evaluations will occur as specified in the Schedule of Assessments.

An end of treatment visit will be performed within 7 days of the last dose of study drug. Upon discontinuation of treatment for any reason, subjects will enter the follow-up period. A

follow-up visit will be performed approximately 30 days after the last dose of study drug. All Adverse Events (AEs) that occur during the safety reporting period (from the first dose of study drug through 30 days after the last dose of study drug or initiation of a new antineoplastic or new investigational agent, whichever occurs first) are to be followed up until resolved or judged to be no longer clinically significant, or until they become chronic to the extent that they can be fully characterized. This may be performed by telephone if applicable. Long-term follow-up visits will be conducted every 30 days for up to 2 years to collect information on survival and subsequent therapies.

During the study, study drug treatment may be interrupted for individual subjects who experience a National Cancer Institute Common Terminology Criteria for Adverse Events (NCI CTCAE) Grade ≥ 3 AE that is attributed to the study drug and cannot be ameliorated with appropriate medical intervention. Study drug may be resumed at the original dose (160 mg/day) or at a reduced dose (120 mg/day or 80 mg/day), after discussion with and approval by the Medical Monitor. Treatment interruption for > 2 weeks must also be discussed with the Medical Monitor.

There will be an initial safety review of the first 21 subjects. After the 21st randomized subject has been treated for 28 days or discontinued from the study (whichever occurs first), unblinded safety data will be evaluated by an independent Data Safety Monitoring Board (DSMB). Emerging safety issues may lead to a decision to change the dose, implement additional safety steps or assessments or terminate the study. Further safety review and details on the process and methods of the safety data review will be provided in the DSMB Charter.

3.3 Randomization

Subjects who meet the inclusion/exclusion criteria will be randomly assigned to receive enzalutamide or placebo using a 2:1 randomization schedule, with two-third of the subjects being randomized to the enzalutamide treatment group and the other one-third of the subjects being randomized to the placebo group. Subjects randomization will be stratified by two primary regions (Asia versus Other), and ECOG performance status (0 versus 1).

Randomization will be performed via an Interactive Response Technology (IRT).

4 SAMPLE SIZE

This sample size was primarily determined to provide sufficient clinical experience to support the design of later-stage clinical development, such as phase 3 studies.

Sample size calculations were performed using EAST 5 software based on the following assumptions:

- 2:1 randomization for enzalutamide vs placebo.
- Median OS for placebo and enzalutamide are 7.0 months and 10.77 months (Hazard Ratio=0.65), respectively.
- A study enrollment period of 18 months and a total study duration of 27 months.

With 109 death events, the study can achieve 80% power to detect a statistically significant difference using 1-sided log-rank test with 10% level of significance. Assuming no loss to follow-up, approximately 144 subjects are needed to reach this number of events.

5 ANALYSIS SETS

In accordance with International Conference on Harmonization (ICH) recommendations in guidelines E3 and E9, the following analysis sets will be used for the analyses.

Detailed criteria for analysis sets will be laid out in Classification Specifications (CS) and the allocation of subjects to analysis sets will be determined prior to database hard lock.

5.1 Full Analysis Set (FAS)

The full analysis set will consist of all randomized subjects, regardless of whether or not subjects received study drug. This will be the primary analysis set for efficacy analyses.

5.2 Safety Analysis Set (SAF)

The Safety Analysis Set (SAF) consists of all subjects who have received at least 1 or partial capsule of study drug.

The SAF will be used for the statistical summary of the safety data.

5.3 Pharmacokinetics Analysis Set (PKAS)

The pharmacokinetic analysis set (PKAS) consists of the subset of the SAF population for which at least one quantifiable enzalutamide or N-desmethyl enzalutamide concentration value is available. Any formal definitions for exclusion of subjects or time-points from the PKAS will be documented in the Classification Specifications. Additional subjects may be excluded from the PKAS at the discretion of the pharmacokineticist. Details will be reported in the CSR.

The PKAS is used for all tables and graphical summaries of the PK data.

5.4 Pharmacodynamic Analysis Set (PDAS)

The pharmacodynamic analysis set (PDAS) will include the subjects from the SAF population for whom sufficient pharmacodynamic measurements (a baseline and at least one post-baseline sample) were collected.

Any formal definitions for exclusion of subjects from the PDAS will be documented in the Classification Specifications.

The PDAS will be used for all analyses of pharmacodynamic data.

6 ANALYSIS VARIABLES

6.1 Efficacy Endpoints

6.1.1 Primary Efficacy Endpoint(s)

6.1.1.1 Primary Analysis

The primary endpoint, overall survival (OS) will be defined as the time from the date of randomization until the documented date of death from any cause. For detailed information for definition, please refer to Appendix 10.1

The null hypothesis is that OS distributions of the 2 arms are equivalent. The alternative hypothesis is that OS is prolonged in enzalutamide arm. The null hypothesis will be tested using a stratified one-sided log-rank test at the 0.10 level (stratified by geographic regions [Asia versus Other] and ECOG performance status [0 versus 1]). The hazard ratio of the treatment effect along with two-sided 95% confidence interval will also be calculated using a Cox proportional hazard model, stratified by geographic regions and ECOG performance status. In addition, an 80% two-sided confidence interval will also be provided to correspond to the 0.1 one-sided alpha level for the primary analysis.

Time to death for a given subject will be defined as the number of days from the date that the subject was randomized to the date of the subject's death. The primary analysis is triggered by the occurrence of the 109th event. All events of death will be included, regardless of whether the event occurred while the subject was still taking study drug, or after the subject discontinued study drug. If a subject has not died, then the data will be censored at the date when the subject was last known to be alive or at the data cutoff date, whichever occurs first.

6.1.1.2 Secondary Analysis

Sensitivity analysis on OS will be done using the unstratified analysis.

6.1.1.3 Subgroup Analysis

The same analysis of the primary endpoint as described in 6.1.1.1 will be conducted using the subgroups of AR (defined as Ventana Total AR Nuclear) patients and other subgroups such as age, gender, geographic region, ECOG status, hepatitis medical history, HepB surface antigen and HCV antibody. Please refer to section 7.8 for details of subgroups of interest.

6.1.2 Secondary Efficacy Endpoints

The Secondary efficacy analyses comparing the effects of Enzalutamide versus placebo will also be performed on progression-free survival (PFS). PFS is defined as the time from the date of randomization until the date of disease progression per RECIST 1.1 or death from any cause on study, whichever occurs first. For detailed information for censoring rules, please refer to Appendix 10.1

6.1.3 Other Efficacy Variables

6.2 Safety Variables

Safety will be assessed by evaluation of the following variables:

- Treatment-emergent adverse events (TEAEs); frequency of TEAEs by system organ class, preferred term, NCI CTCAE grade, frequency of treatment discontinuations due to AEs, severity, and relationship to study drug.
- Clinical laboratory variables (hematology, biochemistry including liver function tests, coagulation parameters and urinalysis, viral load, and pregnancy test).
- Vital signs (systolic and diastolic blood pressure and pulse rate) and body weight.
- 12-lead electrocardiogram (ECG).

6.2.1 Adverse Events

TEAE is defined as an adverse event observed during the treatment emergent period, which is from the first dose date of enzalutamide to 30 days after the last dose date of enzalutamide or the start of subsequent treatment, whichever is first. If the adverse event occurs on Day 1 and the onset check box is marked “Onset after first dose of study drug” or the onset check box is left blank, then the adverse event will be considered treatment emergent. If the adverse event occurs on Day 1 and the onset check box is marked “Onset before first dose of study drug”, then the adverse event will not be considered treatment emergent.

A drug-related TEAE is defined as any TEAE with at least possible relationship to study treatment as assessed by the investigator or with missing assessment of the causal relationship.

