5.5 Adverse Events and Other Safety Aspects

5.5.1 Definition of Adverse Events (AEs)

AEs will be collected from the time of consent until 30 days after the last dose of study drug or initiation of a new antineoplastic or new investigational agent, whichever comes first. An AE is defined as any untoward medical occurrence in a subject administered a study drug or has undergone study procedures and which does not necessarily have a causal relationship with this treatment. An AE can therefore be any unintended sign (including an abnormal laboratory finding), symptom, or disease temporally associated with the use of a study drug, whether or not related to the study drug.

Some countries may have additional local requirements for events that are required to be reported as AEs or in an expedited manner similar to an SAE. In these cases, it is the

Investigator's responsibility to ensure that these AEs or other reporting requirements are followed and the information is appropriately recorded in the source data accordingly.

Adverse events are events that begin or worsen from the time of informed consent through the 30-day Follow-up Period or initiation of a new antineoplastic or new investigational agent, whichever comes first. Treatment-emergent AEs (TEAEs) are events that begin or worsen from the date of first study drug administration through the 30-day Follow-up Period or initiation of new treatment, whichever comes first.

An abnormality identified during a medical test (e.g., laboratory parameter, vital sign, ECG data, physical exam) should be defined as an AE only if the abnormality meets one of the following criteria:

- Induces clinical signs or symptoms
- Requires active intervention
- Requires interruption or discontinuation of study medication
- The abnormality or investigational value is clinically significant in the opinion of the Investigator.

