7.5 Analysis of Safety

7.5.1 Adverse Events

Safety will be assessed through descriptive statistics for the frequency of TEAEs by system organ class, preferred term, and the NCI CTCAE grade, the frequency of treatment discontinuations due to AEs, vital signs, ECG and laboratory evaluations.

The severity of all AEs is to be evaluated by the Investigator based on the NCI CTCAE, version 4.03. All AEs will be coded to preferred term and system organ class using MedDRA. The number and percentage of subjects with TEAEs will be presented by MedDRA system organ class and preferred term, relationship to study treatment, and NCI CTCAE grade. TEAE is defined as an AE observed during the treatment-emergent period, which is from the first dose date of study drug to 30 days after the last dose date of study drug or the start of subsequent treatment, whichever is first. A subject reporting the same AE more than once is counted once and at the maximum severity or strongest relationship to study drug treatment, when calculating incidence.

The number and percentage of TEAEs, serious TEAEs, AEs leading to discontinuation and TEAEs related to study drug will be summarized by system organ class, preferred term and treatment group. The number and percentage of TEAEs by severity will also be summarized. All AEs will be listed.

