7.4.3 Analysis of Exploratory Endpoints

7.5 Analysis of Safety

Safety will be assessed on an ongoing basis by physical examination, measurement of vital signs, laboratory assessments, 12-lead ECGs, and evaluation of TEAEs/serious TEAEs.

Safety analyses will be conducted using the SAF. The SAF is defined as all subjects who have initiated at least 1 or partial capsule of study drug. The treatment emergent period will be defined as the period of time from the first dose date of study drug to 30 days after the last dose date of study drug or the start of subsequent treatment (whichever is first). Only data within this period will be summarized in safety analysis. Safety will be assessed through descriptive statistics for the frequency of adverse events by system organ class (SOC), preferred term (PT), and NCI CTCAE grade, the frequency of treatment discontinuations due to adverse events, vital signs, ECG, and laboratory evaluations.

All safety summaries will be provided using the SAF population.

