TEAEs and the number and percentage of subjects with TEAEs, as classified by SOC and PT will also be summarized by grade and by relationship to study drug. If an adverse event changes in grade or relationship, then the subject will be counted only once with the maximum grade and highest degree of relationship. The adverse event however will be presented in each category they were classified to. If a subject has an event more than once with missing grade/relationship and with non-missing grade/relationship, then the subject will be counted as missing grade/relationship. Drug related TEAEs will be presented in a similar way by grade only.

The Always Serious Terms List is a list of AEs that a Sponsor determines regardless of Investigator assessment are to be captured as serious. Serious TEAEs table will include both investigator reported and Astellas upgraded ones according to Always Serious Terms List. In the listing they will be presented with different flag.

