7.10 Handling of Missing Data, Outliers, Visit Windows, and Other Information

As a general principle, no imputation of missing data will be done. Exceptions are the start and stop dates of AEs and concomitant medication. The imputed dates will be used to allocate the concomitant medication and AEs to a treatment period, in addition to determining whether an AE is/is not treatment emergent. Listings of the AEs and concomitant medications will present the actual partial dates; imputed dates will not be shown.

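### The TEAE flag lacks the begin-or-worsen test of Protocol 5.5.1, and the SAP's Day 1 rule excludes a pre-dose event even if its grade rises on drug

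*SAP*

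**What the plan says.** The documents hold two definitions of a treatment-emergent adverse event.

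- Protocol 5.5.1, the safety section: "Treatment-emergent AEs (TEAEs) are events that begin or worsen from the date of first study drug administration through the 30-day Follow-up Period", or until new treatment starts if that is earlier. This tests for onset or worsening.
- Protocol 7.5.1, the statistical section: "TEAE is defined as an AE observed during the treatment-emergent period, which is from the first dose date of study drug". It has no test for worsening.
- SAP 6.2.1 follows Protocol 7.5.1: "TEAE is defined as an adverse event observed during the treatment emergent period". It adds a check-box rule for events on Day 1. If the box says that onset was after the first dose, or is blank, the event is treatment-emergent. If it says that onset was before the first dose, "then the adverse event will not be considered treatment emergent". No exception is made for a later rise in grade.

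Four other provisions bear on this:

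- Events before dosing are in the database. Protocol 5.5.1 says: "AEs will be collected from the time of consent until 30 days after the last dose of study drug".
- SAP 7.10 uses imputed AE start and stop dates to assign events to a period, "in addition to determining whether an AE is/is not treatment emergent".
- SAP 7.5.1 foresees grade change within one event: "If an adverse event changes in grade or relationship, then the subject will be counted only once with the maximum grade".
- SAP 7.5 says of the treatment-emergent period: "Only data within this period will be summarized in safety analysis".

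**The concern.** Safety is a secondary objective, and the SAP's AE overview and its tables by system organ class and preferred term (all, drug-related, serious, grade 3 or higher, leading to withdrawal) are built on the TEAE flag. If the flag does not match the definition in Protocol 5.5.1, the tables do not describe what that section promises.

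The direction of the error depends on how it arises. Losing events that worsen on drug hides part of any drug effect that takes the form of aggravating an existing symptom. That form is plausible here: Protocol 1.2.2 lists asthenia, fatigue and decreased appetite among events more frequent on enzalutamide than on placebo, and Protocol Appendix 12.2 lists the same events as associated with the disease. Counting unchanged pre-dose events instead adds events unrelated to treatment to both arms, which blurs the comparison. Two programmers working from the same SAP text could produce different tables.

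**Working it through.** No sample size, power or event count bears on this point, so the check compares the definitions case by case.

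First assume that each event stays on one record, with grade changes noted within it, as SAP 7.5.1 allows. SAP 6.2.1 can be read in two ways for events that began before Day 1. Literally, an event still present after first dose is observed in the period. By onset date, only events that start in the period count; the Day 1 box and the date rule in SAP 7.10 point this way.

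| Event (single record) | Protocol 5.5.1 | SAP, literal | SAP, by onset date |
|---|---|---|---|
| (a) Day 1 onset, box ticked pre-dose, grade rises on drug | TEAE | not TEAE | not TEAE |
| (b) Onset between consent and the day before Day 1, ongoing and unchanged after first dose | not TEAE | TEAE | not TEAE |
| (c) Onset between consent and the day before Day 1, grade rises on drug | TEAE | TEAE | not TEAE |
| (d) Onset after first dose | TEAE | TEAE | TEAE |

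Row (a) follows from explicit SAP text and does not depend on the reading. In rows (b) and (c) each reading fails once: the literal one in (b), the onset-date one in (c). Neither fails in both.

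Now assume instead that sites close the original event and enter a new AE whenever it worsens.

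- In (a) and (c) the new record has an onset after first dose, so it is a TEAE under either reading.
- In (b) there is no new record. The onset-date reading correctly leaves the event out; the literal reading still counts it.

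On that data-entry convention, the onset-date reading agrees with Protocol 5.5.1 in all four rows. The documents do not state the convention. Protocol 8.1.5 refers eCRF completion to separate instructions.

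The exposed events are those whose AE record begins between consent and first dose, that is, during screening (Days -21 to -1) or on Day 1 before dosing. The documents give neither the frequency of such events nor the share that worsens, so no count follows.

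**The case against.** The best case on the other side has four parts.

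1. *The SAP did not abandon the protocol.* This stands. A reader might infer that the SAP replaced a settled protocol definition. Protocol 7.5.1 already uses the *observed* wording and SAP 6.2.1 carries it forward; the conflict begins inside the protocol. That changes where the correction is needed, not whether it is.

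2. *A worsening may be an AE in its own right.* Protocol 5.5.1 describes adverse events themselves as beginning or worsening after consent, and Protocol 5.4.5 has worsening examination findings recorded as AEs. If every worsening has its own record, nothing is lost. A reader might therefore go too far in saying that no reading of the SAP reproduces 5.5.1: the onset-date reading would. What remains is that the documents do not state this convention, while SAP 7.5.1 provides for an event that changes grade.

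3. *The exposed group is narrow.* This largely stands. A reader might picture every subject who arrives with fatigue, pain or raised liver tests. Under Protocol 5.2.2, conditions ongoing at consent are medical history with a recorded grade, and a worsening after first dose would be a new AE with on-treatment onset. The explicit exclusion reaches only events that begin on Day 1 before dosing.

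4. *Other outputs give partial cover.* This stands in part. Laboratory grade shifts and ECOG shifts do not use the TEAE flag, the overview has a line for all deaths, and Protocol 7.5.1 has all AEs listed. None of these restores a worsened symptom, such as fatigue, to the AE incidence tables.

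**Conclusion.** The point holds in a limited form. Protocol 5.5.1 on one side and Protocol 7.5.1 with SAP 6.2.1 on the other give different definitions, and the SAP has no worsening test. The certain conflict is the Day 1 exclusion, for an event kept on one record whose grade rises on drug. For onset between consent and Day 1 on one record, the SAP is ambiguous and either reading departs from 5.5.1.

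Two stronger conclusions are not supported. A reader might infer that the SAP both loses worsened events and counts unchanged ones; for onset before Day 1 these errors belong to opposite readings and cannot occur together. A reader might also put a number of subjects on the loss; any such figure would rest wholly on an assumed share, because the documents give none.

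The conclusion rests on one open assumption, that worsening can sit within an existing record. It merits correction because the flag feeds all the TEAE tables and the change is small.

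**What to change.** Use one definition in Protocol 7.5.1 and SAP 6.2.1 that matches Protocol 5.5.1: an AE is treatment-emergent if its onset is after the first dose of study drug, or if it began earlier and its grade increases after the first dose, within the stated window. Then:

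- apply the Day 1 pre-dose exclusion only to events with no later increase in grade;
- put pre-dose events that do not worsen in listings only;
- state whether a worsening is entered as a new AE or as a grade change on the existing record.

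While the sentence is being rewritten, set the window in SAP 6.2.1 by doses of study drug, as SAP 7.5 and Protocol 7.5.1 do. It now refers to doses of enzalutamide, which read literally gives placebo subjects no window.

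The cost is revised wording and one programming condition on onset and grade data already collected. Where a site recorded only the maximum grade, some queries may be needed for the date of worsening. Protocol Appendix 12.9 indicates that the primary analysis has been done. If the SAP is already locked, report this in the clinical study report as a justified change, as SAP section 1 provides.
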